Research Proposal

Title: A Study on the Efficacy and Safety of Accelerated Transcranial Magnetic Stimulation for Obsessive-Compulsive Disorder and Its Underlying Neurological Mechanisms

Principal Investigator: [name]

Protocol Number: 2.0

Protocol Version/Date: 2.0/17 June 2025

I. Research Background

Obsessive-Compulsive Disorder (OCD) is a refractory psychiatric disorder primarily characterised by obsessive thoughts (persistent rumination or doubt concerning an event) and/or compulsive behaviours (repetitive actions, often undertaken to repeatedly verify a particular matter). Its lifetime prevalence ranges from 0.8% to 2.5%¹. The primary treatment approaches for OCD are pharmacotherapy and cognitive behavioural therapy, though their efficacy rates remain approximately 40%–65%. Physical therapies constitute secondary treatment options.

Among these, invasive physical therapies primarily involve anterior capsulotomy and deep brain stimulation. Deep brain stimulation (DBS) is a neurosurgical intervention involving electrode implantation at specific brain locations to deliver therapeutic electrical pulses. The ventral capsule/ventral striatum (VC/VS), subthalamic nucleus, and nucleus accumbens are currently common DBS targets for OCD, effectively alleviating symptoms in patients with severe, treatment-resistant OCD. Multiple randomised controlled trials targeting VC/VS demonstrate approximately 76% response rates in treatment-resistant OCD patients^{2,3}. However, the surgical risks and

financial burden render this approach inaccessible for most individuals. Consequently, non-invasive neuromodulation offers greater universal applicability.

The US Food and Drug Administration (FDA) has approved the H7 coil for deep transcranial magnetic stimulation (dTMS) targeting the medial prefrontal cortex/anterior cingulate cortex for OCD treatment. Following treatment, the response rate (defined as a 30% or greater reduction in symptom severity) among 42 patients receiving active stimulation was 38%, rising to 45% at the one-month follow-up^{4,5,6}. Evidently, existing targets and treatment protocols for rTMS in OCD remain suboptimal.

The inferior frontal cortex (IFC) is closely associated with OCD's characteristic functions of response inhibition, conflict resolution, and uncertainty processing. Research indicates that cognitive behavioural therapy (CBT) can alter IFC volume. This study aims to explore the efficacy of repetitive transcranial magnetic stimulation (rTMS) using novel, individualized IFC targeting combined with symptom-induction techniques.

Reference

- 1 Hirschtritt, M. E., Bloch, M. H. & Mathews, C. A. Obsessive-Compulsive Disorder: Advances in Diagnosis and Treatment. *Jama* 317, 1358-1367, doi:10.1001/jama.2017.2200 (2017).
- 2 Sinai, A. et al. Focused Ultrasound Thalamotomy in Tremor Dominant Parkinson's Disease: Long-Term Results. *J Parkinsons Dis* 12, 199-206, doi:10.3233/JPD-212810 (2022).
- 3 Yamamoto, K. et al. Focused Ultrasound Thalamotomy for Tremor-dominant Parkinson's Disease: A Prospective 1-year Follow-up Study. *Neurol Med Chir (Tokyo)* 61, 414-421, doi:10.2176/nmc.oa.2020-0370 (2021).
- 4 Grant, J. E. Clinical practice: Obsessive-compulsive disorder. *N Engl J Med* 371, 646-653, doi:10.1056/NEJMcp1402176 (2014).

5 Banks, G. P., Heilbronner, S. R., Goodman, W. & Sheth, S. A. A population-normalized tractographic fiber atlas of the anterior limb of the internal capsule: relevance to surgical neuromodulation. *J Neurosurg* 137, 1278-1288, doi:10.3171/2022.1.JNS211935 (2022).

6 Bonelli, R. M. & Cummings, J. L. Frontal-subcortical circuitry and behavior. *Dialogues Clin Neurosci* 9, 141-151, doi:10.31887/DCNS.2007.9.2/rbonelli (2007).

II. Research Objectives and Anticipated Outcomes

- (1) To validate the efficacy of 20Hz rTMS targeting the right IFC in treating treatment-resistant obsessive-compulsive disorder (OCD);
- (2) To investigate whether provocation techniques for obsessive symptoms can enhance treatment efficacy;
- (3) To explore the effects of transcranial magnetic stimulation on cognitive function in OCD patients and its potential physiological mechanisms.

III. Research Content and Methods

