3.1 Overall Study Design and Plan

This study constitutes an open-label, prospective, single-centre investigation.

The intervention employs 20Hz repetitive transcranial magnetic stimulation (rTMS) targeting the right inferior frontal cortex (rIFC). To shorten the treatment cycle, reduce dropout rates, and ensure efficacy, the study will employ the following design: six stimulation sessions per day for five consecutive days, totalling 30 therapeutic stimulation sessions. Magnetic resonance imaging (MRI) scans, cognitive function assessments, and symptom evaluations will be conducted before and after the intervention. Symptom follow-up assessments will occur at two weeks post-treatment, with both symptom and cognitive function follow-ups at four weeks post-treatment. Symptom assessments will be completed by psychiatrists (psychiatrists/psychologists), while the intervention will be administered by trained research assistants.

The study aims to investigate the cognitive regulatory effects of non-invasive interventions. Participants will undergo tailored cognitive assessments based on

individual clinical profiles, with all tasks completed via computer using keyboard or mouse input. These tasks primarily evaluate working memory whilst also assessing attention, learning and memory, executive control, reasoning ability, risk decision-making, affective decision-making, and emotional awareness. Additionally, neuroimaging techniques will be employed to investigate the neural mechanisms underlying cognitive function in OCD patients. Participants will undergo task-related functional magnetic resonance imaging (fMRI) before and after electrical stimulation, performing a series of cognitive tasks related to executive function and affective decision-making during scanning. This will enable comparison of rTMS intervention effects on cognitive function and associated imaging mechanisms.

Data to be recorded for the study include:

Behavioural data: Task-specific behavioural metrics such as accuracy rates and reaction times.

Magnetic resonance imaging data: Acquisition sequences encompass structural imaging, task-state imaging, resting-state imaging, and diffusion tensor imaging.

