3.2 Case Numbers and Grouping Methodology

The study anticipates enrolling 20 subjects with obsessive-compulsive disorder (OCD), all of whom will be assigned to the intervention group for treatment. This is an exploratory clinical study conducted as an open-label trial.

Sample size calculation was performed using G-Power 3.1 with the following parameters:

Effect size d: 1.0

Significance level α : 0.05 (two-tailed)

Power (1- β): 0.95

The calculated minimum sample size required is approximately 16. Considering a 20% clinical attrition rate, 20 participants are planned for enrolment.

IV. Inclusion and Exclusion Criteria

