physical examination, and vital signs. Interviews shall occur during the baseline period, treatment completion period, and follow-up period. The CRF shall include clinical scales required by the study, to be assessed by a clinician. Except during the baseline period, each assessment requires recording the occurrence of adverse events on the case report form. If present, the adverse event report form must be completed in detail. Upon completion of the case report form, the investigator must enter the data into the study computer. Magnetic resonance imaging data and cognitive task data are stored on the study computer, named using the subject identification number and interview period, and saved in a specific format. Data entered into the computer may not be modified by any person during the study period.

This study protocol and data shall be accessible only to medical and statistical experts involved in this trial, participating investigators, and other trial personnel, as well as relevant institutions such as the healthcare facility conducting the trial and the ethics committee. Participants' personal information shall be strictly confidential, with data stored in encrypted computers using participant identification numbers. Data transfer shall be conducted by researchers via encrypted portable hard drives.

Findings from this project may be published in medical journals. Patient information shall remain confidential in accordance with legal requirements and shall not be disclosed unless mandated by relevant legislation. Where necessary, governmental regulatory bodies, hospital ethics committees, and their authorised personnel may access patient records as prescribed.

IX. Statistical Analysis

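### Objective 2 asks whether symptom provocation improves efficacy, but the single-group design has no provocation-free comparison and section 3.1 never mentions provocation

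*Protocol*

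**What the plan says.** Section II lists three numbered objectives. The first is the efficacy of 20 Hz rTMS to the right inferior frontal cortex. The second, listed separately, is "To investigate whether provocation techniques for obsessive symptoms can enhance treatment efficacy". The last sentence of the background in Section I describes the study treatment as individually targeted rTMS "combined with symptom-induction techniques".

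Section 3.1 then describes an open-label study of 20 Hz rTMS to the right inferior frontal cortex, given as "six stimulation sessions per day for five consecutive days, totalling 30 therapeutic stimulation sessions". On timing, it says that "symptom evaluations will be conducted before and after the intervention", with follow-up ratings at two and four weeks. Section VIII agrees: "Interviews shall occur during the baseline period, treatment completion period, and follow-up period".

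Section 3.2 plans 20 subjects, "all of whom will be assigned to the intervention group for treatment". On size it states: "The calculated minimum sample size required is approximately 16", from d = 1.0, two-sided alpha 0.05 and power 0.95, raised to 20 for 20% attrition.

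Section 9.1 mentions inter-group comparisons without defining a second group. Section 9.2 names only comparisons of before with after stimulation.

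**The concern.** To say that provocation enhances efficacy is to say that outcomes are better with it than without it. A study needs some observations without provocation, or a named outside reference, to address that. This protocol describes neither, so one of its three stated objectives has no data that could answer it.

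Two things are at stake. First, if Objective 2 stays, a favourable fall in Y-BOCS could be reported as evidence that provocation helped, although the same fall could come from the stimulation, the passage of time, expectation in an open-label setting, or regression to the mean after selection on a Y-BOCS score of at least 16. Second, the treatment behind the primary endpoint is not described consistently: a reader cannot tell from section 3.1 whether the Y-BOCS result belongs to rTMS or to rTMS plus provocation.

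**Working it through.** **Step 1: look for the contrast.** Each possible source of a with-versus-without comparison, set against the text:

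| Possible source | What the protocol provides |
|---|---|
| Parallel arm | None; all 20 subjects are in one group (section 3.2) |
| Period or crossover | None; one course on five consecutive days (section 3.1) |
| Sessions with and without provocation | None designated; 6 per day × 5 days = 30 sessions, with no distinction among them (section 3.1) |
| Symptom ratings inside the course | None; ratings are before, after, and at two and four weeks (section 3.1; consistent with Section VIII) |
| External or historical control | None named; the 38% and 45% response rates in Section I are background on a different coil and target |
| Analysis text | Section 9.1 mentions groups but defines no second one; section 9.2 is before versus after |

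So 0 of 20 subjects and 0 of 30 sessions are designated provocation-free, and 0 symptom ratings fall within the course.

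**Step 2: look for provocation in the described treatment.** It is named twice, once in the last sentence of the background and once in Objective 2. From Section III to the end of the protocol it does not appear. Three readings follow:

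- Every subject receives it: its effect cannot be separated from that of rTMS, time or expectation.
- No subject receives it: Objective 2 is not addressed at all.
- It varies informally: there is no planned comparison, and the Y-BOCS result applies to an undefined treatment.

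**Step 3: reproduce the stated sample size.** Inputs from section 3.2: d = 1.0, two-sided alpha 0.05, power 0.95. For a one-group (paired) t-test, power = P(|T| > t(0.975; n − 1)), where T is noncentral t with n − 1 degrees of freedom and noncentrality d√n.

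- n = 14: 0.932
- n = 15: 0.949
- n = 16 (noncentrality 1.0 × √16 = 4): 0.962

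The smallest n reaching 0.95 is 16, and 16 / (1 − 0.20) = 20. Both stated figures reproduce.

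**Step 4: check that it is not a two-group figure.** With n per group the noncentrality is d√(n/2) on 2n − 2 degrees of freedom.

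- 8 per group (16 in total): 0.461
- 16 per group: 0.781
- 26 per group: 0.942
- 27 per group: 0.950

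The two-group minimum is therefore 2 × 27 = 54, so 16 fits only a one-group calculation. This is an inference, since section 3.2 does not name the test. The figure of 54 only identifies which calculation was run. It is not a sample size for provocation, because the protocol gives no effect size for that contrast.

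**The case against.** The strongest case on the other side accepts that there is no comparison and argues about weight and wording.

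- *The study is labelled exploratory, and Objective 2 carries no endpoint, test or sample size claim of its own.* True, and the primary Y-BOCS analysis does not depend on it. An exploratory label lowers the evidence required, but it does not supply a comparison.
- *Section 3.1 does not say rTMS alone.* This stands. It is silent on provocation and does not exclude it, so the mismatch with the background is an incomplete description and not a flat contradiction. It still leaves the treatment undefined in the section meant to define it.
- *The protocol does not say that everyone is provoked, so calling the contrast not estimable assumes uniform delivery.* In part. Informal variation is not ruled out, but none is planned, described or tied to a symptom rating, so Objective 2 gains nothing from it.
- *The two-group figures add little.* Agreed as to emphasis; the main point does not depend on power.
- *The analysis plan may deal with it.* It can only analyse what the design produces. Allocation and the content of the intervention belong in the protocol.
- *Objective 2 may simply mean the combined treatment.* Then its wording is wrong, and rewording is the remedy.

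**Conclusion.** The concern holds. As described, the design cannot answer Objective 2, whatever the number of subjects. At most it yields an uncontrolled before-after change for the treatment as delivered. This conclusion rests on reading the objective's verb as comparative and on the protocol's planned structure: one group, one undifferentiated course, no rating inside it, no named external comparator. It does not rest on any power figure. The sample size arithmetic in section 3.2 is correct for the one-group question that it appears to address.

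The inconsistency between Section I and section 3.1 over whether provocation is part of the treatment is a second defect. It bears on the interpretation of the primary endpoint. Both should be put right, because they determine what the trial may conclude.

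**What to change.** 1. Delete Objective 2, or replace it with a plain statement such as: *The separate contribution of symptom provocation to efficacy is not evaluated in this study.* If the intended question is the efficacy of the combined treatment, a non-comparative objective saying so would also remove the fault.
2. Reconcile the last sentence of the background with section 3.1, so that the protocol states whether provocation is part of the intervention to which the Y-BOCS result applies. Which of the two is meant is for the investigators to say.

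Deleting or restating the objective costs wording only: no extra patients, visits or procedures, and no change to the primary endpoint, enrolment or safety collection. The downside is a more modest stated aim. If the reconciliation confirms that provocation is delivered, section 3.1 will also need a description of it.

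Keeping Objective 2 as a comparative question would be a different matter: it would require a described comparison with its own sample size. As an illustration under assumed effects, splitting the planned 20 into 10 and 10 gives two-sided power at alpha 0.05 of 0.185 for d = 0.5, 0.395 for d = 0.8 and 0.562 for d = 1.0, before any attrition.

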3.1 Overall Study Design and Plan

This study constitutes an open-label, prospective, single-centre investigation.

The intervention employs 20Hz repetitive transcranial magnetic stimulation (rTMS) targeting the right inferior frontal cortex (rIFC). To shorten the treatment cycle, reduce dropout rates, and ensure efficacy, the study will employ the following design: six stimulation sessions per day for five consecutive days, totalling 30 therapeutic stimulation sessions. Magnetic resonance imaging (MRI) scans, cognitive function assessments, and symptom evaluations will be conducted before and after the intervention. Symptom follow-up assessments will occur at two weeks post-treatment, with both symptom and cognitive function follow-ups at four weeks post-treatment. Symptom assessments will be completed by psychiatrists (psychiatrists/psychologists), while the intervention will be administered by trained research assistants.

The study aims to investigate the cognitive regulatory effects of non-invasive interventions. Participants will undergo tailored cognitive assessments based on

individual clinical profiles, with all tasks completed via computer using keyboard or mouse input. These tasks primarily evaluate working memory whilst also assessing attention, learning and memory, executive control, reasoning ability, risk decision-making, affective decision-making, and emotional awareness. Additionally, neuroimaging techniques will be employed to investigate the neural mechanisms underlying cognitive function in OCD patients. Participants will undergo task-related functional magnetic resonance imaging (fMRI) before and after electrical stimulation, performing a series of cognitive tasks related to executive function and affective decision-making during scanning. This will enable comparison of rTMS intervention effects on cognitive function and associated imaging mechanisms.

Data to be recorded for the study include:

Behavioural data: Task-specific behavioural metrics such as accuracy rates and reaction times.

Magnetic resonance imaging data: Acquisition sequences encompass structural imaging, task-state imaging, resting-state imaging, and diffusion tensor imaging.

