9.2 Statistical Analysis of Research Data

Magnetic resonance data will be analysed using the SPM toolkit based on MATLAB. Electrophysiological data will be analysed using the fieldtrip toolkit based on MATLAB. Behavioural data will be analysed using MATLAB. Statistical methods will be selected according to research hypotheses and experimental requirements. Statistical software utilised will include MATLAB and SPSS. The primary focus of the study is to compare changes in brain activity (magnetic resonance, electrophysiological) and behaviourally measured cognitive alterations before and after transcranial magnetic stimulation or electrical stimulation.

X. Conflict of Interest

There are no relevant conflicts of interest for this study.

XI. Privacy and Confidentiality

This study will implement stringent privacy protection policies. All information pertaining to this project and its collaborations will be securely safeguarded. No personally identifiable information concerning participants will be disclosed to any external parties under any circumstances. Even if study results are published, participants' personal details will remain confidential.

Participants retain the right to access their personal information and the final research findings. Personal data will be protected throughout all stages of collection, storage, and application (including analysis and comparison).

PI's Signature:

Date:

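### The single-arm before-after design cannot separate an rTMS effect on task performance or task fMRI from the effect of repeating the tasks, although Protocol 3.1 says it will

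*Protocol*

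**What the plan says.** The third objective in Protocol section II is "To explore the effects of transcranial magnetic stimulation on cognitive function in OCD patients and its potential physiological mechanisms". Section 3.1 describes the design: "This study constitutes an open-label, prospective, single-centre investigation". Section 3.2 plans 20 subjects, "all of whom will be assigned to the intervention group for treatment". There is no sham, waiting-list or untreated group.

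Treatment is "six stimulation sessions per day for five consecutive days, totalling 30 therapeutic stimulation sessions". On timing, section 3.1 states: "Magnetic resonance imaging (MRI) scans, cognitive function assessments, and symptom evaluations will be conducted before and after the intervention". A third cognitive assessment comes later, "with both symptom and cognitive function follow-ups at four weeks post-treatment". The computer tasks cover eight named domains, with working memory as the main one, and accuracy and reaction time are given as examples of the measures. Tasks of executive function and affective decision-making are also performed in the scanner before and after stimulation. The battery is adapted to each subject's clinical profile. Section 3.1 then concludes: "This will enable comparison of rTMS intervention effects on cognitive function and associated imaging mechanisms".

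Section 9.1 gives the within-group test as a paired t-test or Wilcoxon signed-rank test. Section 9.2 makes the study's main focus the comparison of brain activity and of "behaviourally measured cognitive alterations before and after transcranial magnetic stimulation or electrical stimulation". The protocol is silent on familiarisation runs, alternate task forms and any allowance for practice.

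**The concern.** For each repeated task, the untreated score is always the first scored exposure and the treated scores are always later ones. Treatment and repetition never vary independently, so the data hold no information with which to divide a change between them. No analysis plan written later can supply the missing contrast.

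On performance tasks, repetition tends to raise accuracy and shorten reaction time, which is also the direction of a hoped-for benefit. In task fMRI, a second exposure may alter activation by itself. Learning tasks are especially exposed, because the first encounter with the material is part of what they measure. The four-week assessment does not resolve this: it is a further exposure, and practice gain can persist.

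At stake is the answer to Objective 3. A before-after improvement could be read as a cognitive effect of rTMS, and imaging changes linked to it as the mechanism, when repetition alone might explain both.

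**Working it through.** **Step 1. The plan's own sample size.** Inputs from Protocol 3.2: d = 1.0, two-sided alpha 0.05, power 0.95, attrition 20%. For a paired t-test, power is the probability that a noncentral t variable with n − 1 degrees of freedom and noncentrality d√n falls beyond the two-sided critical value.

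- n = 15: power 0.949
- n = 16: power 0.962
- Enrolment: 16 / (1 − 0.20) = 20

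The stated 16 and 20 are reproduced. Two independent groups would need 26 per arm by the normal approximation, so the sample size rests on a before-after test within one group, consistent with the design as described.

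**Step 2. What is confounded.**

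| Assessment | Treated? | Scored exposure to a repeated task |
|---|---|---|
| Before treatment | No | First |
| After the five-day course (cognitive tasks and fMRI) | Yes | Second |
| Four weeks after treatment (cognitive tasks) | Yes | Third |

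The expected second-minus-first difference is the rTMS effect plus the repetition effect plus any other change over time. Only the sum can be estimated.

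**Step 3. Illustrative size.** The protocol gives neither a practice gain nor a retest correlation, so both are assumed: a gain g of 0.1 to 0.4 baseline SD and a correlation r of 0.5 to 0.8. With equal SDs at the two visits, the standardised paired change is

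dz = g / √(2(1 − r)).

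At the corners, 0.1 / √(2 × 0.5) = 0.10 and 0.4 / √(2 × 0.2) = 0.63. Putting dz into the test of step 1, with the rTMS effect set to zero, gives the probability of a significant result for one measure:

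| g | r | dz | n = 16 | n = 20 |
|---|---|---|---|---|
| 0 | any | 0 | 5% | 5% |
| 0.1 | 0.5 | 0.10 | 7% | 7% |
| 0.1 | 0.7 | 0.13 | 8% | 9% |
| 0.2 | 0.5 | 0.20 | 12% | 14% |
| 0.2 | 0.7 | 0.26 | 16% | 20% |
| 0.3 | 0.8 | 0.47 | 43% | 52% |
| 0.4 | 0.8 | 0.63 | 66% | 77% |

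At any nonzero gain the probability rises with n, because practice is a bias and not noise. Because the battery is tailored, fewer than 16 subjects may take a given task. The percentages would then be lower for that task, but the bias in the estimated change would be the same.

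**The case against.** The strongest reply is that the study is openly exploratory and single-arm. Section 3.2 says so, Objective 3 is worded as exploration, and section 5.4 lists cognitive data among the exploratory endpoints. The Y-BOCS endpoint and its sample size do not depend on this point. All of that stands and limits the weight of the point. It does not rescue the sentence in 3.1, which claims that treatment effects can be compared; and section 9.2 makes before-after brain and cognitive change the main focus, so the matter is not peripheral.

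The wording in 9.2 is itself descriptive: it speaks of alterations before and after stimulation and attributes no cause. The overclaim therefore lies mainly in 3.1, with Objective 3 leaning the same way.

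It is also fair that the percentages rest on assumed inputs and are sensitive to them. At the low end they barely exceed 5%, and the top figures are the extreme corner of the range. Nor is a practice gain to be expected everywhere: the protocol gives no reason to expect one in risk or affective decision-making or in emotional awareness.

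A reader might infer three stronger things that the document does not support:

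- That practice gain will be reported as cognitive benefit. This is a prediction; what can be shown is that the two cannot be told apart.
- That the retest is about a week after baseline. The course lasts five days, but the interval between assessments is not stated.
- That no familiarisation run is planned. The protocol is silent on how the tasks are given, and a task manual could include one. It would reduce practice gain without removing the confounding.

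**Conclusion.** The point holds as a limit on interpretation. With every subject treated and every later score on a repeated task a repeat exposure, the design cannot distinguish an rTMS effect from practice gain on performance tasks, or from repetition effects in task fMRI. The sentence in 3.1 claims a property that the design lacks. This follows from the design alone and needs no assumed figure. It does not extend to structural, resting-state or diffusion imaging as far as task practice is concerned.

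The size is illustrative. On the assumptions in step 3 the chance of a significant change with no rTMS effect is about 7% to 66% per measure with 16 subjects and 7% to 77% with 20. The true figure could lie anywhere in or outside that range, depending on the task. The change is worth making before baseline testing starts, since a first exposure cannot be repeated.

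**What to change.** **Wording, needed in any case.** Reword the sentence in 3.1 and Objective 3 so that they describe change in cognitive performance and brain activity after rTMS. State that practice is not separated from stimulation and that no causal conclusion about cognition will be drawn. This costs nothing beyond the edit.

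**Reducing the bias.**

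- Give each subject a short unscored familiarisation run, outside the scanner, of the tasks in that subject's own battery, using practice material that appears in no scored session.
- For learning-type tasks, rehearse only the instructions and the response format, so that the first exposure to the material is not used up.
- Use parallel stimulus sets, in an order rotated across subjects, at the baseline, post-treatment and four-week assessments.

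The cost is some patient time before baseline and some task programming, with no additional scans. These steps reduce the confounding but do not remove it, so they do not replace the rewording.
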